### 5.5.5. Maintenance

Maintenance chemotherapy with vincristine, DS-1594b, and prednisone for approximately 24 months beginning at Dose level 0 or lower dose level if prior toxicity required dose reduction of agents (titrate to keep ANC  $> 0.5 \times 10^9/L$  and platelet count  $\geq 30 \times 10^9/L$ ) (See [Table 8](#)[Table 8](#) below):

- Vincristine 2 mg IV on Day 1 approximately every 28 days.
- Prednisone 50 mg orally daily on Days 1 to 5 approximately every 28 days with vincristine.
- DS-1594b continuously, twice daily (or daily) every 28 days at the same dose received during induction/consolidation.
- For DS-1594b dose adjustments, see Section 6.
- Suggested maintenance chemotherapy dose adjustments are in [Table 8](#)[Table 8](#) below.

Formatted: C-Hyperlink

Formatted: C-Hyperlink

**Table 8: Maintenance Chemotherapy Dose Adjustments**

Level	Vincristine (mg)	Prednisone (mg)
0	2	50
-1	1	40
-2	0	30

- Prednisone
  - Dose should remain at 50 mg unless steroid myopathy or other significant toxicity occurs.
  - Prednisone is not required to be dose adjusted for hyperglycemia.
  - Further reductions beyond what is shown in [Table 8](#)[Table 8](#) may be allowed if recommended by the treating physician and after discussion with the PI.
- Vincristine
  - Decrease by one dose level for Grade 2 peripheral neuropathy persisting longer than 2 weeks and bilirubin  $> 2 \text{ mg/dL}$  and  $\leq 3 \text{ mg/dL}$ .
  - Discontinue for Grade 3 or greater peripheral neuropathy persisting longer than 2 weeks, including Grade 3-4 ileus suspected to be related to vincristine, or bilirubin  $> 3 \text{ mg/dL}$ .

Formatted: C-Hyperlink

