**Table 7: Dose levels for miniHCVD, and DS-1594b**

Dose Level	miniHCVD	DS-1594b
-1	As published  miniHCVD regimen	Lower dose of DS-1594b as recommended by SRC
0 (Starting dose)	As published miniHCVD regimen	One dose level below the RP2D of DS-1594b from the Phase 1
1	Not applicable	RP2D of DS-1594b from the Phase 1

DS-1594b orally twice daily (or daily, dependent on results from dose escalation phase). In each cycle, DS-1594b will be taken daily continuously.

Variations in dose reductions of the individual chemotherapy or the administration of venetoclax or supportive care dose schedules other than those suggested below are allowed in the best interest of subjects. Such subjects should be discussed with the principal investigator. Dose escalations of chemotherapy above those outlined in the protocol; however, are not allowed. Variations in infusion times due to minor differences in IV bag overfill/underfill and institutional procedure on flushing chemotherapy lines will not result in protocol deviation.

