#### **5.5.4. Suggested Standard Dose Reductions/Modifications/Discontinuations:**

- Vincristine 1 mg IV Days 1 and 11 (50% reduction) if:
  - Bilirubin  $> 2$  mg/dl and  $\leq 3$  mg/dl
  - Clinically significant grade 2 peripheral neuropathy persisting greater than 2 weeks.
  - Eliminate vincristine for Grade 3-4 peripheral neuropathy, including Grade 3-4 ileus suspected to be related to vincristine, or bilirubin  $> 3$  mg/dL.
- Methotrexate:
  - Consider reduction by 25% to 50% for Grade 3 or worse mucositis with previous methotrexate course.
  - Reduce by 50% for calculated creatinine clearance 10-50 mL/min, if  $< 10$  mL/min, hold methotrexate.
  - Reduce by 25% to 75% for delayed excretion and/or nephrotoxicity with previous methotrexate course.
  - Reduce by 50% for pleural effusion or ascites (drain effusion if possible).
- **Non-hematological toxicity**

- If Grade 3 or 4 non-hematologic toxicity is at least possibly attributable to DS-1594b, dose interruption of DS-1594b is required. Subjects who experience drug-related Grade 3 non-hematological toxicity may be given a subsequent course one dose level below the previous course, but the subject must have recovered to Grade  $\leq 1$  before start of the next course. If a subject has drug-related Grade 4 non-hematological toxicity, he/she may receive a subsequent courses at one reduced dose level after resolution of toxicity to Grade  $\leq 1$ , only if approved by the PI based on the clinical significance of the toxicity and only if subject has had derived a benefit from the therapy. The dose of DS-1594b can be decreased during a cycle, at the discretion of treating physician and PI, for chronic Grade 2 non-hematological toxicity. Other dose modifications may be considered as clinically indicated with documentation and approval of the PI.

- **Hematologic toxicity**

- Dose interruptions or modifications will be made for Grade 4 hematological toxicities, only if considered at least possibly related to DS-1594b and not related to underlying disease or the use of chemotherapy, as determined by the treating physician and the study PI. Subjects with baseline neutropenia or those who have significant bone marrow involvement may be particularly at high risk.

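### The maintenance vincristine reduction rule in Section 5.5.5 joins two toxicities with *and*, so the trigger for the 1 mg step is wrong or at best ambiguous

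*Combined protocol and SAP*

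**What the plan says.** Section 5.5.5 sets maintenance vincristine for Cohort D as follows: "Vincristine 2 mg IV on Day 1 approximately every 28 days". Table 8 gives three vincristine levels: 2 mg (level 0), 1 mg (level -1) and 0 mg (level -2).

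Two bullets under Table 8 govern changes to that dose:

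- **Reduction:** "Decrease by one dose level for Grade 2 peripheral neuropathy persisting longer than 2 weeks and bilirubin" above 2 and up to 3 mg/dL.
- **Discontinuation:** Grade 3 or worse "neuropathy persisting longer than 2 weeks, including Grade 3-4 ileus suspected to be related to vincristine, or bilirubin" above 3 mg/dL.

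Section 5.5.4 covers the intensive phase. Its reduction rule opens with "Vincristine 1 mg IV Days 1 and 11 (50% reduction) if" and then has one bullet for bilirubin above 2 and up to 3 mg/dL and another for neuropathy: "Clinically significant grade 2 peripheral neuropathy persisting greater than 2 weeks". Its stopping rule is "Eliminate vincristine for Grade 3-4 peripheral neuropathy, including Grade 3-4 ileus suspected to be related to vincristine, or bilirubin" above 3 mg/dL.

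The maintenance rules are not mandatory. Section 5.5.5 introduces them with "Suggested maintenance chemotherapy dose adjustments are in" Table 8. The text after Table 7 begins "Variations in dose reductions of the individual chemotherapy" and allows departures from the suggested schedules when they serve the subject.

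**The concern.** The reduction bullet puts two different toxicities, one neurological and one hepatic, into a single condition joined by *and*. On the literal reading, a subject in maintenance with only one of them has no listed step between full dose and discontinuation. For bilirubin alone, nothing is listed from above 2 up to 3 mg/dL, and above 3 mg/dL the drug is stopped. The intermediate 1 mg level in Table 8 is then never reached by listed rule.

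What is at stake is consistent handling of the same toxicity. One physician reads the bullet literally and finds no listed 1 mg step for persistent Grade 2 neuropathy alone. Another reads it as a list of separate reasons and finds one. Vincristine is repeated about every 28 days for roughly two years, so the rule may be consulted more than once for the same subject.

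**Working it through.** No sample size, power or error-rate figure is involved, so the check is a comparison of the text plus a count of cases.

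**Step 1. How each rule joins the two toxicities.**

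| Rule | Section | Neuropathy condition | Bilirubin condition | How joined |
|---|---|---|---|---|
| Reduce to 1 mg, intensive phase | 5.5.4 | Clinically significant Grade 2, over 2 weeks | >2 to ≤3 mg/dL | Separate bullets after *if* |
| Stop, intensive phase | 5.5.4 | Grade 3–4, including ileus | >3 mg/dL | *or* |
| Reduce by one level, maintenance | 5.5.5 | Grade 2, over 2 weeks | >2 to ≤3 mg/dL | *and* |
| Stop, maintenance | 5.5.5 | Grade 3 or worse, over 2 weeks, including ileus | >3 mg/dL | *or* |

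The maintenance reduction rule is the only one of the four that uses *and* between the toxicities. Section 5.5.4 prints no *or* between its two reduction bullets, but separate bullets under one *if* are most naturally read as alternatives.

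**Step 2. Cases in which the step is listed.** Let N be Grade 2 neuropathy lasting over 2 weeks and B be bilirubin >2 to ≤3 mg/dL.

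| Combination | Literal *and* | *Or* reading |
|---|---|---|
| Neither | No step | No step |
| N only | No step | 1 mg |
| B only | No step | 1 mg |
| N and B | 1 mg | 1 mg |

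The step is listed in 1 of 4 combinations under *and*, and in 3 of 4 under *or*. The readings differ in 3 − 1 = 2 of 4, which are the two single-toxicity cases. This counts cases. It is not a frequency of events.

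**Step 3. Size of the dose difference.** From Table 8, level 0 minus level -1 = 2 mg − 1 mg = 1 mg per dose.

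**Step 4. Does another part of the protocol settle the reading?** None says whether the maintenance reduction needs both toxicities or either one. Section 5.5.5 lets maintenance start below level 0 when earlier toxicity has already forced a reduction. That protects subjects reduced in the intensive phase. It does not help a subject whose neuropathy or raised bilirubin first appears in maintenance.

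**Step 5. Could the difference from Section 5.5.4 be deliberate?** The sections differ in other ways. Section 5.5.4 asks for clinically significant Grade 2 neuropathy and Section 5.5.5 does not. Section 5.5.4 also covers dosing on Days 1 and 11, whereas maintenance has one dose about every 28 days. A deliberate difference cannot be excluded, but no reason for one is given.

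**The case against.** The best reply is that *for X and Y* is an ordinary way to list two indications. On that reading the bullet already lets either toxicity act alone. The thresholds fit this: the bilirubin band for reduction ends where the stopping band begins, and Grade 2 neuropathy sits just below Grade 3. That looks like a two-step ladder for each toxicity, and Section 5.5.4 sets out such a ladder for the same drug with the same bilirubin limits. So the surrounding text also helps a reader infer what was probably meant.

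This reading is possible, and it is why ambiguity is the minimum claim. It does not clear the text. The very next bullet uses *or* for the same pair of toxicities, so a careful reader has grounds to think the change of word is meant. The other *and* in the bullet, between the two bilirubin limits, does require both parts to hold. That is weaker evidence, because it only bounds a range on one variable.

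The second reply is that discretion already covers the gap. The adjustments are suggestions. The text after Table 7 and Sections 5.5.2.1, 5.5.4 and 6.8 all allow other modifications, generally after discussion with the principal investigator. The carry-over clause in Section 5.5.5 also protects subjects whose dose was reduced earlier. All of this stands. The bullet does not oblige full dosing, and the 1 mg level stays available as a permitted variation. This limits the harm to inconsistent handling, but a suggested dosing rule should still have one meaning.

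**Conclusion.** The concern holds. As written, the maintenance reduction bullet either requires two toxicities where one should be enough, or leaves the reader to guess. The protocol does not say which reading applies.

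The impact is minor: 1 mg per dose, in the two single-toxicity cases, for Cohort D subjects who reach maintenance. Cohort D enrols at most 32 subjects (Section 3.3), and the documents do not say how many will reach maintenance or develop either toxicity, so no subject count or cumulative dose can be given. Sample size, stopping rules and the primary endpoint are unaffected.

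The conclusion rests on two assumptions: that the separate bullets in Section 5.5.4 are alternatives, and that no undocumented clinical reason exists for requiring both toxicities in maintenance.

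**What to change.** In the vincristine reduction bullet of Section 5.5.5, replace *and bilirubin* with *or bilirubin*, so that either toxicity alone triggers the one-level reduction. If full alignment with Section 5.5.4 is wanted, also add *clinically significant* before the Grade 2 neuropathy condition. If the investigators did intend both toxicities to be required, insert *both* so that the rule has a single reading.

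The cost is one word, plus two optional words, at the next amendment. Table 8 and all other sections stay as they are.

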### 5.6. Concomitant Medications

#### 5.6.1. Concomitant Medications – Subject Supportive and Safety

The use of any concomitant medication/therapies deemed necessary for subject supportive care and safety are permitted, with the exception of those outlined below. Other leukemia directed therapy including systemic chemotherapy or biologic response modifiers are not permitted during

the study except for those specified in the eligibility criteria. A course of radiation therapy as required in the best interest of the patient if approved by the PI/Co-PI. No other investigational agent for the treatment of AML is allowed during the study. Antiemetics may be used for the prevention or treatment of nausea and vomiting.

Administration of other antineoplastic agents is prohibited for subjects while on this study with the following exceptions:

- intrathecal (IT) therapy for subjects with controlled CNS leukemia at the discretion of the PI,
- Since the effect of DS-1594b may be mediated by differentiation, this effect may be delayed, use of hydroxyurea (any dose) for subjects with rapidly proliferative disease is allowed on study and before the start of study therapy and will not require a washout. These medications will be recorded in the case-report form.

#### **5.6.2. Medications that may prolong the QTc interval**

Medications that may prolong QTc interval and have a known risk of inducing Torsades de Pointes should be avoided unless it is vital for the care of the subjects:

- Concomitant use of DS-1594b with drugs known to have a high risk of increasing the QTc interval, and drugs known to increase the QTc interval that are also primarily metabolized by CYP3A should be avoided. See Appendix [Table 28](#)[Table 28](#).

Formatted: C-Hyperlink

#### **5.6.3. Concomitant Medications Requiring Caution**

- Based on nonclinical assessment, DS-1594b is primarily metabolized by CYP3A. Caution should be exercised with concomitant use of drugs that are moderate inhibitors or inducers of CYP3A (Appendix [Table 30](#)[Table 30](#)). The actual dose, actual start/end date and time of dosing for these concomitant medications should be recorded on the eCRF.
- DS-1594b is shown to inhibit P-gp activity in vitro with estimated IC50 value of 1.79 μM. Alternative therapies that are not P-gp substrates should be considered. If concomitant use of DS-1594b and P-gp substrates is unavoidable, separate DS-1594b administration by at least 6 hours before or after the administration of oral narrow therapeutic index P-gp substrates (e.g. digoxin, tacrolimus) to minimize the potential for interactions.
- DS-1594b was shown to inhibit BCRP and OCT1 activities in vitro with estimated IC50 value of 1.94 μM and 0.489 μM, respectively. Alternative therapies that are not BCRP or OCT1 substrates should be considered. If concomitant use of DS-1594b and BCRP or OCT1 substrates is unavoidable, caution should be exercised when co-administered with DS-1594b (Appendix [Table 30](#)[Table 30](#)).
- The concurrent use of a H2-antagonist or an antacid is allowed, but the H2-antagonist must be administered 10 hours before or 2 hours after the DS-1594b dose, and the antacid must be administered 2 hours before or 2 hours after the DS-1594b dose.

Formatted: C-Hyperlink

Formatted: C-Hyperlink

- Caution is advised with concurrent use of proton pump inhibitors, as exposure of DS-1594b may be reduced. The dose, start/end date of dosing for these concomitant medications should be recorded on the eCRF.
- Caution is advised with concurrent use of ethinyl estradiol containing contraceptives, as in vitro studies of DS-1594b have demonstrated the potential for time-dependent inhibition of CYP3A. If ethinyl estradiol containing contraceptives are used, counsel subjects and monitor for adverse events related to potential increased ethinyl estradiol exposure, such as venous thromboembolism.
- Drugs that should be used with caution are included in Appendix [Table 30](#)[Table 30](#).

Formatted: C-Hyperlink

#### 5.6.4. Prohibited Concomitant Medications:

- Co-administration of DS-1594b with drugs that are CYP3A and CYP2C19 substrates known to have narrow therapeutic index should be avoided, unless there are no alternative therapies or if the drugs are considered by the investigators as vital for the care of the subjects.
- Strong inhibitors or inducers of CYP3A may affect the clearance of DS-1594b, and this may impact its potential efficacy or increase the risk of side effects. Therefore, strong CYP3A inhibitors (e.g. posaconazole, voriconazole) or inducers (e.g. rifampin) should be restricted in the initial stage of the study until DDI assessments have been conducted post-MTD/RP2D determination to characterize this risk.
- P-gp substrates that have narrow therapeutic indices should be avoided.
- Drugs that should be restricted is included in Appendix [Table 29](#)[Table 29](#).
- For the DDI sub-study with anti-fungal agents, medications known to induce or inhibit CYP3A (moderate/strong inhibitors/inducers) must be discontinued or substituted one week prior to the first dose of DS-1594b, or must be temporarily interrupted during the course of the DDI sub-study of 17 day duration (Appendix [Table 28](#)[Table 28](#) and [Table 31](#)[Table 31](#)).
- For the food effect sub-study, gastric reducing agents such as proton pump inhibitors should be discontinued one week prior to the first dose of DS-1594b or must be temporarily interrupted during the sub-study of 14-day duration (Appendix [Table 31](#)[Table 31](#)).
- Refer to the package inserts of venetoclax and azacitidine for prohibited concomitant medications related to venetoclax and azacitidine (Cohort C).

Formatted: C-Hyperlink

Formatted: C-Hyperlink

Formatted: C-Hyperlink

Formatted: C-Hyperlink

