### 3.2.3.2. Sub-study Design

Following dosing in Phase 1 Dose Escalation and MTD declaration, approximately 12 additional subjects will be enrolled into a drug-drug interaction (DDI) sub-study within the Phase 1 portion of the study at a predetermined dose level (at least 50% below the RP2D, as recommended by the SRC) to assess the effect of multiple doses of antifungal agents (i.e. posaconazole [N ~ 6], voriconazole [N ~ 6]) that are strong CYP3A inhibitors, on the steady-state PK of DS-1594b. Based on preliminary assessment using physiologic-based modeling, the magnitude of PK increase of DS-1594b ranges from 30% (with posaconazole) to 2-fold (with voriconazole).

This estimate will be further assessed based on emerging clinical and nonclinical data and the information will be provided to the SRC for consideration in dose selection. Nonetheless, the dose will be at least 50% below the declared RP2D. These subjects can be the same subjects included in the Phase 1 expansion for RP2D determination.

This DDI sub-study is a single sequence, crossover design. Enrollment will complete on the posaconazole sub-study before enrollment will begin on the voriconazole sub-study. Subjects will receive twice-daily or daily oral dosing of DS-1594b alone at the assigned dose from Cycle 1 Day 1 to Cycle 1 Day 8. On Cycle 1 Day 9 to Cycle 1 Day 18, subjects will receive the same assigned DS-1594b dose with either (a) 300 mg oral posaconazole twice on Cycle 1 Day 9 and once daily on Cycle 1 Day 10 to Cycle 1 Day 18 or (b) 400 mg oral voriconazole twice on Cycle 1 Day 9 and 200 mg twice daily from Cycle 1 Day 10 to Cycle 1 Day 18.

The anti-fungal agents are planned to be given for 10 consecutive days as stated above to ensure steady-state is reached in order to maximize inhibitory effect on CYP3A-mediated metabolism of DS-1594b. After completion of the sub-study (Cycle 1 Day 18 is the last day of the sub-study), subjects will continue with DS-1594b dosing alone starting on Cycle 1 Day 19. PK sampling timepoints of DS-1594b are outlined in [Table 17](#)[Table 17](#).

Formatted: C-Hyperlink

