**Note:** If the use of posaconazole is essential for subject care during the dose escalation phase (i.e. prior to MTD/RP2D declaration), the subject can enter the DDI sub-study sooner, starting from the third dose escalation cohort. Voriconazole is not allowed as DDI perpetrator prior to MTD declaration given it is a more potent CYP3A inhibitor compared to posaconazole. To avoid interference with the DLT evaluation period (first 28-day cycle), subjects will receive oral twice daily or daily dosing of DS-1594b alone at the assigned dose for the entire Cycle 1. Starting on Cycle 2 Day 1 to Cycle 2 Day 10, subjects will receive either the same assigned DS-1594b dose provided that dose level has been declared safe from the DLT evaluation, or at one dose level lower with 300 mg oral posaconazole twice on Cycle 2 Day 1 and once daily on Cycle 2 Day 2 to Cycle 2 Day 10. After completion of the sub-study (Cycle 2 Day 10 is the last day of the sub-study), subjects will continue with DS-1594b dosing alone starting on Cycle 2 Day 11. PK sampling timepoints of DS-1594b for these subjects are outlined in [Table 18](#)[Table 18](#). These subjects will contribute to the overall sample size of ~ 12 for DDI sub-study.

Formatted: C-Hyperlink, Font: Italic

The entry criteria for subjects in DDI sub-study will be the same as all other subjects, except for additional concomitant medications restrictions for CYP3A modulators and gastric reducing agents (see Section 4.2 ).

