#### **3.2.4.2. Sub-Study Design**

Following MTD declaration, approximately 6 additional subjects will be enrolled into a food effect sub-study to evaluate the effect of a standard meal on the steady-state PK of DS-1594b.

This sub-study follows a single sequence, crossover design. Subjects will receive oral twice-daily or daily dosing of DS-1594b at a predetermined dose level (at least 50% lower than the RP2D) within 0.5 hours after a standard meal (breakfast and dinner), defined as one containing 600 kcal and 30% fat (~21g fat), from Cycle 1 Day 1 to Cycle 1 Day 8. Subjects should refrain from food and drink, except water, 2 hours before dosing (except for breakfast and dinner) and 2 hours after dosing.

From Cycle 1 Day 9 to Cycle 1 Day 18, subjects will receive the same DS-1594b dose under fasting conditions (i.e. subjects refrain from food and drink, except water, for 2 hours before dosing and for 2 hours after dosing). See Section 5.1.2 (under “food effect sub-study only”) for more details regarding dose administration guidance. On days when PK blood samples will be taken, DS-1594b dosing and meal regimens will be administered at the investigational site. After completion of the sub-study (Cycle 1 Day 18 is the last day of sub-study), subjects will continue with DS-1594b dosing under fasting conditions, same as patients not in sub-study (DS-1594b dosing at least 1 hour before or 2 hours after a meal) starting on Cycle 1 Day 19.

**Note:** The entry criteria will be the same as the preceding cohorts, except for additional concomitant medications restrictions for CYP3A modulators and gastric reducing agents (see Section 4.2). PK sampling timepoints of DS-1594b are outlined in [Table 19](#)[Table 19](#).

Formatted: C-Hyperlink

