### 3.2.4.3. Sub-Study PK Evaluability Criteria

Subjects should meet the following minimum criteria to be considered evaluable for the food effect assessment. PK non-evaluable subjects will be replaced.

- On Cycle 1 Day 8 and Cycle 1 Day 18, subject takes DS-1594b according to the assigned dose.
- Subject has an interpretable PK profile following administration of the assigned dose of DS-1594b on Cycle 1 Day 8 and Cycle 1 Day 18.
- Subject takes DS-1594b under the assigned dose and prandial conditions (first 7 days under fed state, then under fasted state afterwards) for at least 5 consecutive days prior to full PK sampling days on Cycle 1 Day 8 and Cycle 1 Day 18.
- Subject does not vomit within 4 hours after DS-1594b dosing on full PK sampling days.

For toxicity monitoring in each group of the DDI sub-study and food effect sub-study we will use the elimination boundaries in [Table 4](#)[Table 4](#) for BOPN design.

Formatted: C-Hyperlink

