**Food effect sub-study only:**

- Subjects in this sub-study do not follow bullet (4) above but the bullets below for prandial condition.
- For the morning doses from Cycle 1 Day 1 to Cycle 1 Day 8, DS-1594b will be administered immediately (within 0.5 hours) following a standard breakfast defined as one containing 600 kcal and 30% fat (~ 21g fat). Subjects should refrain from food and drink, except water, for at least 2 hours after dosing; for the evening doses (12 hours apart from morning dose) (applicable for BID dosing only), DS-1594b will also be administered immediately (within 0.5 hours) following a standard dinner (same meal content as breakfast). Subjects should refrain from food and drink, except water, for 2 hours before dosing (except for breakfast and dinner) and for 2 hours after dosing.
- Starting from Cycle 1 Day 9 to Cycle 1 Day 18, DS-1594b should be administered under fasting condition (i.e. subjects should refrain from food and drink, except water, for 2 hours before dosing and for 2 hours after dosing). After completion of the sub-study (Cycle 1 Day 18 is the last day of sub-study), subjects will continue with DS-1594b dosing under fasting conditions, same as patients not in the food effect sub-study (DS-1594b dosing at least 1 hour before or 2 hours after a meal) starting on Cycle 1 Day 19.

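### Section 5.6.4 gives the food effect sub-study, and its PPI interruption, 14 days although the fasted profile is on Cycle 1 Day 18; related day references in 5.6.4, 8.4 and 9.4.9 also conflict with the sampling tables

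*Combined protocol and SAP*

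**What the plan says.** **Restriction on interacting drugs.** In the food effect bullet of section 5.6.4, PPIs are to be stopped one week before the first dose of DS-1594b or "must be temporarily interrupted during the sub-study of 14-day duration". In the DDI bullet next to it, moderate and strong CYP3A modulators are to be stopped or substituted one week before, or "must be temporarily interrupted during the course of the DDI sub-study of 17 day duration".

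**Sub-study calendar.** Section 3.2.4.2 gives fed dosing on Cycle 1 Days 1 to 8 and fasted dosing on Days 9 to 18, and states "Cycle 1 Day 18 is the last day of sub-study". Section 5.1.2 agrees: "Starting from Cycle 1 Day 9 to Cycle 1 Day 18, DS-1594b should be administered under fasting condition". The evaluability criteria in 3.2.4.3 require the assigned prandial condition "for at least 5 consecutive days prior to full PK sampling days on Cycle 1 Day 8 and Cycle 1 Day 18". For DDI subjects entering after MTD declaration, 3.2.3.2 says "Cycle 1 Day 18 is the last day of the sub-study". For those entering earlier, on posaconazole only, it says "Cycle 2 Day 10 is the last day of the sub-study".

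**Profiles and analysis.** Table 19 samples full food effect profiles on Day 8 (fed) and Day 18 (fasted), and 9.4.9.1 reports the Day 18 to Day 8 ratio. Section 8.4 lists the steady-state food effect parameters for Days 8 and 15, and 9.4.9 lists Day 15 as the food effect day for the concentration plots.

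**Restriction elsewhere.** Exclusion criterion 4.2o bars subjects who cannot stay off PPIs or moderate CYP3A modulators until the sub-study period ends. Table 31 lists the prohibited drugs with no day limit. The Table 30 footnote says without a day limit that moderate CYP3A modulators are prohibited for sub-study subjects.

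**The concern.** Both sub-studies compare two steady-state profiles within the same subject, so an interacting drug must be absent at both. Section 5.6.3 warns that a PPI may lower DS-1594b exposure. A site that interrupted a PPI and restarted it after 14 days would have it present at the fasted profile and absent at the fed one. That would pull down the Day 18 to Day 8 ratio and look like higher exposure with food. The sub-study has about 6 subjects, and its stated purpose is to help choose the prandial condition, partly because venetoclax must be taken with food. For a DDI subject who entered before MTD declaration, a moderate CYP3A modulator could likewise be present at one profile and not the other.

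The Day 15 references are a separate problem. Section 9.4.9 says the parameters listed in 8.4 will be estimated, so the analysis text asks for a food effect profile that is never drawn. Section 8.4 lists no food effect parameters for the day that the primary analysis uses.

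**Working it through.** **Inputs.** Cycle length is 28 days (5.1.2). Food effect profiles are on C1D8 and C1D18 (Table 19, 9.4.9.1). DDI profiles are on C1D8 and C1D18 for entry after MTD declaration (Table 17), and on C1D8 and C2D10 for earlier entry (Table 18). Stated durations are 14 days (food effect) and 17 days (DDI), both in 5.6.4.

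**Formulas.** Study day = 28 × (cycle − 1) + day. Elapsed days = last − first. Inclusive days = last − first + 1.

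1. *The plan's 17 days, DDI entry after MTD declaration.* C1D1 to C1D18: 18 − 1 = 17 elapsed, 18 inclusive. The stated figure is reproduced as elapsed days.
2. *The plan's 14 days, food effect.* The calendar is the same, C1D1 to C1D18: 17 elapsed, 18 inclusive. Neither count gives 14. An end on Day 15 would give 15 − 1 = 14 elapsed, which is the day named in 8.4 and 9.4.9.
3. *Shortfall counted from C1D1.* Fourteen elapsed days end on Day 15, leaving 18 − 15 = 3 days. Fourteen inclusive days end on Day 14, leaving 18 − 14 = 4 days. With once-daily dosing the profile closes with the Day 19 pre-dose sample, so the gaps are 19 − 15 = 4 and 19 − 14 = 5 days.
4. *Dependence on the start day.* The two food effect profiles are 18 − 8 = 10 elapsed (11 inclusive) days apart, so a 14-day window that began late enough would contain both. Days 5 to 18, for example, are 14 inclusive days. But 5.6.4 ties the interruption to the sub-study, which starts on Day 1, and a later start would leave early fed dosing days uncovered. The shortfall in step 3 therefore rests on a Day 1 start.
5. *DDI entry before MTD declaration.* C2D10 is study day 28 × (2 − 1) + 10 = 38. From C1D8 this is 38 − 8 = 30 elapsed, 31 inclusive days. Both exceed 17, so no 17-day window contains both profiles, wherever it starts. From C1D1 the span is 37 elapsed, 38 inclusive days.
6. *Day 15 against Table 19.* The Day 18 profile has 8 samples from pre-dose to 8 h, plus either the 12 h sample (twice daily) or the Day 19 pre-dose sample (once daily): 8 + 1 = 9. Day 15 has 0.

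**The case against.** The strongest reply is that the design is not in doubt. The operative instruction in 5.6.4 is to interrupt for the sub-study, and the day count only describes it; 3.2.4.2 fixes the last day as Day 18. Criterion 4.2o excludes anyone who cannot stay off these drugs to the end, and the restrictions in Table 31 and the Table 30 footnote carry no day limit. Section 5.6.5 says what to do when a prohibited drug is taken in error. PPI dates go on the eCRF, evaluability requires an interpretable profile, and non-evaluable subjects are replaced, so a breach could be found and handled. The DDI part is narrower still: earlier entry is optional and limited to subjects for whom posaconazole is essential, and their number is not given and could be zero.

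Most of this stands, and it is why the point is minor. It does not remove the need for correction. Criterion 4.2o governs entry, whereas 5.6.4 is the rule applied on treatment, and a site restarting a PPI after 14 days could say that it had followed 5.6.4. The evaluability lists do not name PPIs or other CYP3A modulators. Nothing in 4.2o bears on the Day 15 text, which cannot be carried out as written.

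A reader might infer that the food effect result will be biased, or that no restriction reaches Day 18. The documents support neither. A reader might also infer that an abandoned Day 15 design left these figures behind. The match in step 2 makes that plausible, but the documents do not say so. The meal records for C1D1 and C1D8 in 8.4.1 are not a further error, because both are fed days.

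**Conclusion.** The point holds as a minor internal inconsistency, in three parts.

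- **Food effect duration:** the 14 days in 5.6.4 is wrong under either way of counting. If the interruption starts on C1D1, it ends 3 or 4 days before the fasted primary profile.
- **Second food effect profile:** Day 15 in 8.4 and 9.4.9 conflicts with Table 19 and 9.4.9.1, which both use Day 18.
- **DDI duration:** 17 days is right, as elapsed days, for entry after MTD declaration. It cannot cover both profiles for the optional earlier posaconazole entrants.

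Bias would require a site to use the interruption option and follow the day count over the other sections. The documents give no PPI or CYP3A effect size under these conditions, so the size of any bias cannot be derived. The MTD and the Phase 2 endpoints are unaffected.

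**What to change.** **Section 5.6.4.** Delete both durations. State that a temporary interruption starts no later than the washout that 4.2o requires before the first dose of DS-1594b: at least 2 days for PPIs and at least one week for CYP3A modulators. State that it continues until the last PK sample of the second full profile:

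- food effect sub-study, and DDI entry after MTD declaration: C1D18, or the C1D19 pre-dose sample with once-daily dosing;
- DDI entry before MTD declaration: C2D10, or the C2D11 pre-dose sample with once-daily dosing.

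In the same edit, reconcile the PPI washout, which is one week in 5.6.4 and at least 2 days in 4.2o.

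**Sections 8.4 and 9.4.9.** Change Cycle 1 Day 15 to Cycle 1 Day 18 for the food effect sub-study.

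**Section 4.2o.** Its end-of-sub-study wording can stay. A note covering the next-morning sample under once-daily dosing is optional.

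The cost is wording in 5.6.4, 8.4 and 9.4.9, and in 4.2o if the washout is settled there. No visit, sample, procedure or subject is added.
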